16.2. Sample Size Determination

Interim Analysis will be conducted by an independent DMC after 18-week 6MWD data are available from 75 patients. The purpose of the interim analysis is to stop the trial for an early efficacy or futility conclusion or to continue the trial to 150 or 188 - patients (total randomized is higher to account for an anticipated 20% dropout rate). Group sequential early stopping criteria and sample size re-estimation methodology are further described in the statistics section of this protocol. They are constructed to control overall type 1 error at 0.025, 1-sided. Simulations assuming true underlying mean treatment difference in 6MWD ranging from 30-70 meters and standard deviations from 50 to 75 meters yielded >87% power for all cases except the most extreme case (mean difference 30 meters and SD 75), for which power was ~71%.

Subjects who do not comply with the required device adherence, as well as who do not meet the study entry criteria at Week 2, will be withdrawn from the study.

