16.3. Efficacy Analyses

16.3.1. Primary Efficacy Endpoint

The primary endpoint is to evaluate the efficacy of iNO as measured by the placebo-adjusted change in 6-minute walk distance (6MWD) from baseline to 18 weeks. The average of the two 6MWDs at Week 2 (after run-in) will be used as the baseline value for analysis of data. The

6MWD at Week 2 should be obtained on all subjects, even if the subject does not qualify to enter into the treatment phase.

The primary statistical test for the primary endpoint will be performed using a repeated measures mixed model with the baseline stratification factor (i.e., the prostanoid usage status), - treatment arm, week, and treatment-by-week interaction as the main effects. As a covariate, baseline 6MWD assessment will be included in the model. In case the normality assumption is substantially violated (i.e., graphical assessment of residuals from the analysis model and the Shapiro-Wilk test statistic graphical assessment of the residuals from the analysis model and), the primary efficacy endpoint will be analyzed using the van Elteren test stratified by the prostanoid usage status. Least Squares mean differences, standard errors, 95% confidence intervals will be derived from the analysis model.

Exploratory analyses will be performed to evaluate the effects of demographics and baseline characteristics on the efficacy response with appropriate statistical methods. Subgroup analyses based on study drug usage, background therapies, demographics and baseline characteristics, as well as other study compliance status will be conducted. Additional statistical methods such as mixed effects model and Cochran–Mantel–Haenszel (CMH) test (for dichotomized response analysis) may be utilized in the exploratory analyses.

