16.5. Interim Analysis

A formal interim analysis is planned in this study as follows:

1. Stop for futility (null hypothesis is accepted; there is no difference between iNO and Placebo).
2. Stop for efficacy (null hypothesis is rejected; there is difference between iNO and Placebo favoring iNO).
3. Sample size determination (decision to use blinded or unblinded data).
4. Stop in case of safety concerns. Safety concerns may be some imbalances in adverse events frequency which is not in favor of iNO. No formal statistical guideline is provided for this purpose, the sponsor relies on the medical expertise of DMC members.
5. Continue the trial with the planned sample size until next stage if point 1, 2 or 4 not apply.

The following two designs will define the interim analysis strategy:

- 1) Design 1: Groups Sequential Design (for efficacy part)
- 2) Design 2: Sample Size Re-estimation (SSR) (for futility and sample size re-estimation)

The interim analysis schedule planned as follows:

Schedule	Requirement
1st	After 75 patients complete 18 Weeks of blinded treatment phase.
Final	After 150/188 (depending on CP and PP) patients complete 18 Weeks of blinded treatment phase.

Traditional group sequential design (GSD) alpha spending function $\Gamma = -3$ (Hwang, Shih, deCani, 1990) is used to control the overall type 1 error at 0.025, 1-sided. The interim analysis rule (Table 7) is as follows.

Table 7: Interim and Final Analysis Rules

Category	Rule
Efficacy	At first interim analysis (after 75 patients), if the one-sided $p < 0.0046$ then the study will stop for efficacy (Wald Statistics)
Efficacy	At final analysis (after 150 patients or 188 patients depending on CP and PP), if the one-sided $p < 0.0229$ then the study will yield an efficacy conclusion. (based on CHW Statistics)
Futility	If conditional power (CP) or predictive power (PP) $\leq 10\%$ then the study stops for futility.
Continue	If $10\% < CP$ and $PP < 30\%$ then trial continues to 150 patients.
SSR	If $30\% \leq CP$ or $PP < 80\%$ then the sample size required to boost the CP or PP to 80% is computed. If this sample size exceeds 188 (upper limit) then the study continues at $N = 150$ else to 188.
Continue	If CP and $PP \geq 80\%$ then the trial continues to $N = 150$ patients

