This is the "promising zone" sample size re-estimation (SSR) design of Mehta & Pocock (2011), which uses the Cui, Hung, Wang (1999) method of analysis to combine the test statistics for the separate analyses of the IA and post-IA parts of the trial, if the trial does not stop at IA.

The final analysis is via weighted Z statistic using equal weights for the IA and post IA test statistics. It requires $p < 0.0229$ 1-sided for statistical significance to control the overall type 1 error level at 0.025 1-sided per the $\Gamma = -3$ error spending function (Hwang, Shih, deCani 1990).

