### Missing Data Imputation Rules:

Missing data will not be imputed for primary analysis.

The results will be presented in terms of LS means and the difference between LS means, with associated confidence interval and p-value.

Standard descriptive statistics for two separate categories ((1) increase in 6MWD from baseline at Week 18 and decrease in 6MWD from baseline at Week 18) will be presented along with the visit-wise 6MWD.

This analysis will be performed on Intention to treat (ITT), Per-Protocol (PP) and Modified Intention to treat (mITT).

Analysis performed on ITT will be considered as primary.

The within-subject error is assumed to have an unstructured (UN) covariance matrix. However, if the fit of the unstructured (UN) covariance structure fails to converge, then the following options will be tried in order until convergence is reached.

- 1) Toeplitz with Heterogeneity (TOEPH)
- 2) Autoregressive with Heterogeneity (ARH(1))
- 3) Toeplitz (TOEP)
- 4) Autoregressive (AR(1))
- 5) Compound Symmetry (CS)

If model still doesn't converge then this will be highlighted and discussed in the BDR meeting and an appropriate covariance structure to be used will be agreed. The denominator degrees of freedom will be estimated using a Kenward-Roger approximation. The pairwise treatment differences will be estimated as differences between the least-squares means and tested using an F-test based on the Type III sums of squares.

The SAS code for the MMRM analysis is provided below for interim analysis.

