**Table 35: Interim and Final Analysis Rules:**

Category	Rule
Efficacy	At interim analysis (after 75 patients), if the one-sided $p < 0.0046$ then the study will stop for efficacy (Wald Statistics)
Efficacy	At final analysis (after 150 patients or 188 patients depending on CP and PP), if the one-sided $p < 0.0229$ then the study will yield an efficacy conclusion. (based on CHW Statistics)
Futility	At interim analysis, if conditional power (CP) or predictive power (PP) $\leq 10\%$ then the study stops for futility.
Continue	At interim analysis, if $10\% < CP$ and $PP < 57.2\%$ then trial continues to 150 patients.
SSR	At interim analysis, if $57.2\% \leq CP$ or $PP < 80\%$ the sample size is increased to $N=188$ . The lower bound of the promising zone interval was calculated based on the minimum treatment effect needed to achieve 70% or higher CP.
Continue	At interim analysis, if $CP$ and $PP \geq 80\%$ and 1-sided $p > 0.0046$ , then the trial continues to $N = 150$ patients.

This is the "promising zone" sample size re-estimation (SSR) design of [Mehta & Pocock \(2011\)](#), which uses the [Cui, Hung, Wang \(1999\)](#) method of analysis to combine the test statistics for the separate analyses of the IA and post-IA parts of the trial, if the trial does not stop at IA.

The final analysis is via weighted Z statistic using equal weights for the IA and post IA test statistics. It requires  $p < 0.0229$  1-sided for statistical significance to control the overall type 1 error level at 0.025 1-sided with  $\gamma = -3$  error spending function ([Hwang, Shih, deCani 1990](#)).

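### The primary effect is to be reported as the ordinary MMRM difference with a 95% interval, although the decision uses group-sequential boundaries; the estimate and interval should match the look at which the trial ends

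*Protocol*

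**What the plan says.** **Reporting.** Protocol 16.3.1: "Least Squares mean differences, standard errors, 95% confidence intervals will be derived from the analysis model". SAP 7.3.1: "The results will be presented in terms of LS means and the difference between LS means, with associated confidence interval and p-value". The PROC MIXED code in the same SAP section, introduced as the interim code, asks for confidence limits on the treatment-by-visit means and sets no level, so the default 95% applies. Degrees of freedom are Kenward-Roger.

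**Decision.** Protocol 16.2 says of the stopping and re-estimation rules: "They are constructed to control overall type 1 error at 0.025, 1-sided". At the interim (Protocol 16.5), "if the one-sided $p < 0.0046$ then the study will stop for efficacy". At the end, "It requires $p < 0.0229$ 1-sided for statistical significance to control the overall type 1 error level at 0.025 1-sided". SAP 8.0 adds: "The final analysis is via weighted Z statistic using equal weights for the IA and post IA test statistics". The last look comes "After 150/188 (depending on CP and PP) patients complete 18 Weeks of blinded treatment phase". SAP 7.3.1 drops the CHW statistic if re-estimation is blinded, and leaves that choice until shortly before the interim.

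**What is absent.** The CHW formulas in SAP 7.3.1 cover the test statistic only. Neither document names a repeated, stage-wise or CHW-based interval, or a bias-adjusted estimate. The SAP 11.0 table of changes from the protocol is empty.

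**The concern.** The plan protects the test and leaves the estimate as if the trial had one fixed look. A trial that stops at 75 patients has been selected for a large observed difference, so the ordinary estimate tends to be too high and its interval too optimistic. At the final look a 95% interval uses 1.960 while the test needs 1.997, so a borderline trial could report an interval above zero beside a failed test. The difference in metres is the headline result, and it is most exposed in the outcome the sponsor hopes for, early success. An interval chosen after a conflicting result would not be credible, so it should be fixed in advance.

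**Working it through.** **Inputs.** Overall one-sided alpha 0.025 and Hwang-Shih-DeCani gamma = -3 (Protocol 16.5, SAP 8.0); interim at 75, final at 150 or 188; 1:1 allocation; true differences of 30 to 70 m and SD 50 to 75 m (Protocol 16.2); increase to 188 when conditional power (CP) is 57.2 to 80%, and a futility stop at CP of 10% or less (SAP Table 35).

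**Assumptions.** Known SD, no missing data, CP under the current trend used in place of predictive power, independent stage statistics, and no overrun patients at an early stop.

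**1. Reproduce the plan's figures.** Alpha spent at t = 75/150 = 0.5 is 0.025 × (1 - e^1.5)/(1 - e^3) = 0.025 × 3.482/19.086 = 0.00456, which matches 0.0046 (Z = 2.605). Solving the bivariate normal with correlation √0.5 for the remainder gives a final level of 0.02288, which matches 0.0229 (Z = 1.997). CP values in SAP Table 22 reproduce (0.739, 0.934, 0.991, 0.964). Power at 30 m/SD 75 is 71.3% if the whole 30 to 80% zone goes to 188 and futility is not applied, and 69.5% with the SAP zone, against the stated 71% or so. With futility applied it is 65 to 68%.

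**2. Estimate after an early efficacy stop.** The interim standard error is SE1 = SD × √(4/75), which is 17.32 m at SD 75 and 11.55 m at SD 50. A stop therefore needs an observed difference of at least 2.605 × 17.32 = 45.1 m at SD 75, or 30.1 m at SD 50. With k = 2.605 - true/SE1, the chance of stopping is 1 - Φ(k), and the mean estimate given a stop is true + SE1 × φ(k)/(1 - Φ(k)). At 30 m/SD 75, k = 0.873, so the chance is 19% and the mean is 30 + 17.32 × 1.42 = 54.7 m.

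**3. Coverage of the ordinary 95% interval** (SAP zone, futility as written, integration over the interim Z and simulation):

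| True / SD (m) | Early efficacy stop | Mean estimate after stop (m) | Overall coverage |
|---|---|---|---|
| 30 / 75 | 19% | 54.7 | 94.1% |
| 30 / 60 | 33% | 45.2 | 93.9% |
| 40 / 75 | 38% | 57.2 | 93.8% |
| 30 / 50 | 50% | 39.3 | 93.5% |
| 50 / 50 | 96% | 51.1 | 96.4% |
| 70 / 75 | 92% | 72.7 | 96.0% |

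Given an early stop at 30/75, coverage is 87%. With futility not enforced, coverage over the planning range is 94.55 to 96.4%. The protocol's different re-estimation zone changes these figures by less than 0.1 point.

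**4. Interval against test.**
- **N = 150.** The equal weights make CHW and the pooled Z the same. Take Z1 = 1.90 and Z2 = 0.90 at SD 75. Then Z = 2.80/√2 = 1.980 and p = 0.0239, so the test fails. The estimate is 1.980 × 12.25 = 24.25 m, with 95% interval 0.24 to 48.25 m. At 1.997 the lower limit is -0.21 m and the conflict disappears.
- **N = 188.** The weights differ. Take Z1 = 1.80 (CP 0.78) and Z2 = 1.03. CHW is 2.83/√2 = 2.001, p = 0.0227, so the test succeeds. The pooled Z is √(75/188) × 1.80 + √(113/188) × 1.03 = 1.935, and the ordinary lower limit is (1.935 - 1.960) × 10.94 = -0.3 m.
- **Frequency.** At 30/75 the interval excludes zero while the test fails in 0.8% of trials with futility applied (about 0.01% of trials at N = 188), and in about 1.05% without. The reverse conflict occurs in at most 0.06%.

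**5. Check of the matched interval.** Using ±2.605 SE at the interim and the CHW pivot ±1.997 at the end, coverage is at least 95.2% at every effect tried, lower-limit error is at most 2.5%, and no conflict with the test is possible. Example: a stop at Z1 = 3.0, SD 75. The ordinary estimate is 52.0 m (18.0 to 85.9), the repeated interval is 6.8 to 97.1, and the mean-bias-adjusted estimate is 48.4 m.

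**The case against.** The best reply is that no decision is affected: the boundaries reproduce and control type I error, so this is reporting around a valid test. That is true, and it limits the weight of the point. A reader might infer that the trial's error control is broken; the documents do not support that.

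Four further replies also stand in part.

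- **Coverage.** It is tempting to say the 95% interval fails to cover 95%. It over-covers at large planning effects. Futility not enforced is also the version closest to the stated power, and there the shortfall within the planning range is under half a point.
- **Size of bias.** The 25 m inflation is conditional on an early stop in the case the protocol itself calls most extreme. Averaged over all trials at 30/75, the bias is +0.2 m with futility applied and +2.4 m without.
- **Cause of conflict.** One might blame the changed sample size or the CHW weights. Nearly all conflicts are simply 1.960 against 1.997, and they occur at N = 150.
- **Quantiles.** Kenward-Roger limits use t quantiles. Assuming about 70 and 140 degrees of freedom, coverage at 30/75 rises to 94.5% and the conflict rate falls to 0.43%.

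None of this removes the inflated estimate and weak coverage after an early stop at the smaller planning effects. Nothing in either document addresses that.

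**Conclusion.** The concern holds in a limited form, and the sponsor should act on it. The plan prescribes an unadjusted estimate and interval for a design with an early efficacy stop.

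The early-stop estimate is the main harm: about 55 m for a true 30 m at SD 75 (82% too high, 87% coverage, about 19% of trials), shrinking to about 4% at 70 m/SD 75. Overall under-coverage is secondary, at most about 1.5 points in the planning range, and depends on enforcing futility. Conflict with the test is rare, at about 1% of trials or fewer. If re-estimation is blinded, the CHW mismatch falls away, but the early-stop bias and the 1.960 against 1.997 gap remain.

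The figures rest on the normal approximation and the other assumptions listed with the calculation.

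**What to change.** In SAP 7.3.1 and 8.0, define the primary interval as the one that inverts the test used at the look where the trial ends:

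- **Stopped at the interim:** the repeated interval at the 0.0046 boundary (±2.605 SE).
- **Final analysis:** an interval at one-sided 0.0229 (95.42% two-sided). Base it on the CHW pivot if N was raised to 188 using unblinded data, and on the MMRM otherwise.
- **After an early stop:** also report a mean-bias-adjusted estimate, meaning the true difference at which the design's average ordinary estimate equals the one observed. A stage-weighted or stage-wise median-unbiased estimate will not do, because at the first look it equals the ordinary estimate. The adjustment is partial: at Z1 = 2.65 and SD 75 it moves 45.9 m to 42.4 m.
- **Descriptive:** keep the ordinary MMRM difference and 95% interval, labelled as such. Amend Protocol 16.3.1 to agree.

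The cost is wording and a short calculation, with no new data, visits or patients. The interval is about 2% wider at N = 150 (1.997/1.960) and about one third wider after an early stop (2.605/1.960).

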16.3.2. Secondary Efficacy Endpoints

The secondary efficacy endpoints include:

1. TTCW*: The time (in days) from start of treatment to first event (first day the event is noted), with iNO as compared to placebo, measured from baseline to week 18. TTCW event is defined as any of the following:
 - a. Death (all-cause mortality)
 - b. Atrial septostomy
 - c. Hospitalization due to worsening of PAH (adjudicated)
 - d. Start of new specific PAH treatment (endothelin receptor antagonists [ERAs], phosphodiesterase type-5 [PDE-5] inhibitors or prostanoids), an increase in the dose of an ERA or PDE-5, increase in the dose or frequency of an inhaled prostanoids, or an increase in the dose of an intravenous or subcutaneous prostanoids by >10%.
 - e. Decrease of >15% from baseline or > 30% compared with the last study related measurement in 6MWD and should be confirmed by a repeat measurement performed at least 14 days later
 - f. Worsening of WHO Functional Class (e.g., from Class II to Class III or IV, OR Class III to Class IV); and should be confirmed by a repeat assessment at least 14 days later
2. Change in WHO Functional Class, with iNO as compared to placebo, from baseline to 18 weeks.

The TTCW endpoint will be analyzed with log-rank test stratified by the prostanoid usage status. The censoring time points for the analyses include the time points at which subjects drop out of the study or complete the study without any of the specified events.

The WHO Functional Class endpoint will be analyzed with the same method as that for the primary endpoint. Change from baseline to week 18 will also be evaluated as an exploratory analysis.

16.3.3. Tertiary Endpoints

1. Change in health-related quality of life (using SF-36 version 2 health survey), with iNO as compared to placebo, from baseline to 18 weeks
2. Change in pulmonary hemodynamics (i.e., cardiac output [CO], cardiac index [CI], mean pulmonary artery pressure [mPAP], mean pulmonary capillary wedge pressure [mPCWP], systolic pulmonary artery pressure [sPAP], diastolic pulmonary artery pressure [dPAP], pulmonary vascular resistance [PVR], and oxygen saturation by pulse oximeter [SpO₂], mixed venous O₂, and right atrial pressure [RAP]) measured by right heart catheterization (RHC), with iNO as compared to placebo, from baseline to 18 weeks, in a subset of subjects (approximately 50), at selected sites
3. Change in echocardiogram measurements right ventricular function (including right ventricular fractional area change, systolic pulmonary artery pressure [sPAP], tricuspid annular motion/tricuspid annular plane systolic excursion, tricuspid annular systolic velocity, and Tei index) and left ventricular function (including left ventricular ejection fraction [LVEF], LV size, and improvement in LV early diastolic relaxation velocity), with iNO as compared to placebo, from baseline to 18 weeks, in a subset of subjects (approximately 50), at selected sites
4. Change in NT-proBNP, with iNO as compared to placebo, from Screening to 18 weeks
5. Change in Borg dyspnea score immediately following 6MWT, with iNO as compared to placebo, from baseline to 18 weeks
6. Change in 6MWD as related to degree of drug adherence, with iNO as compared to placebo, from baseline to 18 weeks
7. The number of subjects with unsatisfactory clinical response, with iNO as compared to placebo, from baseline to 18 weeks. Defined as: WHO Functional Class III or IV symptoms with no improvement in 6MWD
8. Number of subjects undergoing heart-lung or lung transplantation, number of subjects listed for transplantation, and deaths while awaiting transplantation, from baseline to 18 weeks
9. Medical resource utilization, with iNO as compared to placebo, from baseline from baseline to 18 weeks

For continuous (or numerical) response endpoints, the statistical analyses will be performed using the same method as that for the primary efficacy endpoint. Binary (or dichotomized) response endpoints will analyzed by CMH test stratified by the prostanoid usage status.

16.3.4. Multiplicity Adjustment

To control the Type-1 error rate at a level of 0.025 1-sided, a hierarchical gate keeping procedure will be applied to test the significant difference between the treatment groups in the primary and secondary endpoints in the following order:

1. 6MWD
2. TTCW
3. WHO Functional Class

Each test will be evaluated at the appropriate p-value alpha spending function. The procedure will stop if lack of significance is found for any of the variables and the remaining test(s) in the sequence (as mentioned above) will also be concluded as non-significant.

16.3.5. Handling Missing Data

Missing data imputation for primary endpoint:

For primary analysis, i.e. change from baseline at Week 18, missing data will not be imputed.

The following missing data imputation techniques will be employed for sensitivity analyses of primary endpoint.

- 1) Last Observation Carry Forward (LOCF) approach will be applied for subjects not withdrawing trial due to adverse events, for subjects withdrawing trial due to adverse events (including deaths), worst value (for e.g. zero for 6MWD) will be assigned at EOS visit.
- 2) Worst-case imputation approach I (i.e. impute the missing value for a subject with worst value (within the subject) for all subjects who withdraw prematurely for any reason. The value of zero for 6MWD will be imputed for all deaths.
- 3) Worst-case imputation approach II (i.e., impute the missing value for a subject in the active and Placebo dose group by the worst result of all subjects with non-missing assessments in their respective assigned dose groups). The value of zero for 6MWD will be imputed for all deaths.
- 4) Worst-case imputation approach III (i.e. impute the missing value for a subject in the active dose group by the worst result of all subjects with non-missing assessments in the same active dose groups and impute the missing value for a subject in placebo group by his/her last available assessment prior to the missing assessment. The value of zero for 6MWD will be imputed for all deaths.

Missing data imputation for secondary endpoint:

For all the other efficacy endpoints, the last observation carry forward (LOCF) approach will be used in handling the missing data as that used in the EARLY study ([Galiè 2008](#)).

